## 8.5 Description of Statistical Analyses

### 8.5.1 General Considerations

A general description of the statistical methods to be used to analyze the efficacy and safety data is outlined below. Prior to locking the database, a detailed IAP will be developed.

Continuous variables will be summarized descriptively using the number of observations, mean, SD, median, first quartile (Q1), third quartile (Q3), minimum, and maximum. Categorical variables will be summarized using frequency counts and percentages. The denominator for the percentages will be the total number of subjects in the treatment group and analysis set being presented, unless otherwise specified (e.g., on some occasions, percentages may be calculated based on the total number of subjects with available data at a particular time point).

Tests of treatment effect on each of the two co-primary efficacy endpoints will be conducted at a one-sided  $\alpha$ -level of 0.0125, to maintain a study-wide one-sided  $\alpha$ -level of 0.025. P-values and the two-sided CIs (97.5% or 95% as appropriate) will be presented where applicable. Actual p-values will be interpreted based on the multiple testing strategy, as specified in this protocol, and detailed further in the IAP. Treatment comparisons for each data type are described in later sections. Alternative or additional statistical methods may be used as appropriate as outlined in the IAP.

Data from all investigative sites will be pooled for all planned analyses. Analysis of individual site findings or country findings will be considered if necessary. For those measures that are analyzed using change from Baseline scores, observed scores may also be presented descriptively.

For SRI-4 or SRI-6 response at Week 52 (Week 24), a subject experiencing flare or CS dose increase during Weeks 41 to 52 (Weeks 17 to 24), or a subject with a missing response at Week 52 (Week 24), will be considered a non-responder. Four sensitivity analyses of the primary analysis are planned: (1) non-responder imputation for subjects discontinuing treatment for reasons due to efficacy/safety, with available observations used (in MMRM or multiple imputation) for subjects discontinuing treatment for reasons unrelated to efficacy/safety or completing treatment with missing response at Week 52, (2) unadjusted analysis, (3) completer analysis, and (4) per-protocol analysis (i.e., excluding subjects with clinically important protocol violations). Additional procedures for handling missing, unused, or spurious data, and sensitivity analyses exploring the impact of missing data will be described in the IAP.

The IAP will provide definitions of Baseline measurement as needed for change from Baseline endpoints.

Treatment compliance will be assessed in terms of the percentage of the actual doses taken relative to the number of scheduled doses and summarized by descriptive statistics.

All subjects will be included in individual subject data listings.

Any changes in the data analysis methods described in the protocol will require an amendment only if the change affects a principal feature of the protocol. Any other changes to the planned data analysis that does not require a protocol amendment will be described in the IAP and the CSR.

CCI

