## 8 Statistics

### 8.1 Sample Size

A sample size of 103 evaluable subjects per group provides 80% power at the  $\alpha = 0.025$  one-sided significance level to detect

- an absolute improvement of 20% in Week 52 SRI-4 response proportion for M2951-treated subjects relative to placebo-exposed subjects, among subjects with SLEDAI-2K total score  $\geq 6$  at Screening, assuming a placebo response proportion of 40%,

or

- an absolute improvement of 25% in Week 52 SRI-6 response proportion for M2951-treated subjects relative to placebo-exposed subjects, among subjects with SLEDAI-2K total score  $\geq 10$  at Screening (i.e., HDA), assuming a placebo response proportion of 30%,

assuming that each co-primary endpoint is tested via a chi-squared test of the odds ratio (OR) for treatment effect at the 0.0125 one-sided level, and assuming that approximately 50% of randomized subjects are in the HDA group. If the absolute improvement in Week 52 SRI-6 response proportion in HDA subjects is only 20%, the power is 76%. Approximately 108 subjects will be randomized per treatment group to protect against a loss of information due to drop-out (for reasons other than efficacy/safety) of 5% over 52 weeks. Given the randomization ratio 1:1:1:1, the total sample size required for the primary analysis is planned to be 432 subjects.

Approximately 432 subjects will enter the main study. Assuming an 80% rate of continuation to LTE, approximately 346 subjects are expected to enter the LTE Period.

The Japan cohort size was determined to provide a reliable evaluation of consistency in the Week 52 SRI-4 response proportion between the non-Japan and Japan regions. Assuming that:

- (i) the Week 52 SRI-4 response proportion in the placebo group is 0.40 for both the non-Japan and Japan regions,
- (ii) the Week 52 SRI-4 response proportion due to each of the 3 M2951 dose groups is 0.60 for both regions, so that the true underlying effect size is 0.20 for both regions,
- (iii) a total evaluable sample size of 412 (i.e., 309:103 randomization for M2951: placebo) is involved in analysis of the two regions,

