## 8.5.2 Analysis of Primary Endpoints

The primary analysis of SRI-4 response at Week 52 among all subjects in the primary analysis cohort, and SRI-6 response at Week 52 among HDA subjects in the primary analysis cohort, will be an estimate of OR, together with associated two-sided 95% CI and p-value (testing null hypothesis  $H_0: OR = 1.0$ ), comparing each M2951 dose group to placebo, based on a logistic model for the odds of a given SRI response in the appropriate population, with M2951 dose group or placebo group as a factor and adjustment for covariates based on randomization strata. Additional covariates may be included in the model as specified in the IAP. In the primary analysis of SRI-4 or SRI-6 response at Week 52, a subject experiencing flare or CS dose increase during Weeks 41 to 52, or a subject with a missing response at Week 52, will be considered a non-responder.

The primary analysis of the co-primary efficacy endpoints will be based on the mITT analysis set, with supportive analyses based on the ITT and PP analysis sets, if the size of these analysis sets differ substantially ( $> 10\%$ ) from the size of the mITT analysis set.

The Family-Wise type 1 error rate (FWER) due to the co-primary endpoints and multiple M2951 dose group comparisons versus placebo will be controlled at the two-sided  $\alpha = 0.05$  level via a tree

gatekeeping procedure. The four hypotheses associated with the comparisons involving the co-primary endpoints and the two highest dose groups will form the first family of hypotheses in the tree. This family will be tested via the truncated Hochberg procedure, with truncation fraction pre-specified in the IAP. The multiple-testing procedure for the remainder of the tree, including the hypotheses associated with the comparisons involving the co-primary endpoints and the lowest dose group will be specified in the IAP.

A test for monotonic dose-response relationship, between ordered M2951 dose and SRI-4 response OR relative to placebo, will be performed as a supportive analysis. Similarly, a test for monotonic dose-response relationship, between ordered M2951 dose and SRI-6 response OR relative to placebo, will be performed as a supportive analysis in the HDA subgroup.

Descriptive statistics for SRI-4 response, and for SRI-6 response in the HDA subgroup, will be provided for each treatment group by time point.

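### The one-sided 0.0125 level in Section 8.5.1 and the 80% power in Section 8.1 belong to a different testing rule from the four-hypothesis truncated Hochberg family in Section 8.5.2

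*Protocol*

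**What the plan says.** **Per-endpoint rule.** Section 8.5.1: "Tests of treatment effect on each of the two co-primary efficacy endpoints will be conducted at a one-sided" level of 0.0125, said to maintain a study-wide one-sided 0.025, with two-sided intervals of 97.5% or 95% as appropriate. The same paragraph adds that p-values will be interpreted under the multiple testing strategy in the protocol and the IAP.

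**Power.** Section 8.1, repeated in the Synopsis: "A sample size of 103 evaluable subjects per group provides 80% power at the" one-sided 0.025 level to detect either "an absolute improvement of 20% in Week 52 SRI-4 response proportion for M2951-treated subjects relative to placebo-exposed subjects" (placebo 40%) or "an absolute improvement of 25% in Week 52 SRI-6 response proportion for M2951-treated subjects relative to placebo-exposed subjects" (placebo 30%, high disease activity subgroup, half of the subjects), "assuming that each co-primary endpoint is tested via a chi-squared test of the odds ratio (OR) for treatment effect at the 0.0125 one-sided level". With a 20-point SRI-6 effect the stated power is 76%. The number randomised is 108 per group, to cover 5% unrelated drop-out.

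**Family rule.** Section 8.5.2, and also Section 5.1 and the Synopsis: the family-wise error over endpoints and doses is controlled at two-sided 0.05 by tree gatekeeping. The first family holds four hypotheses, the two co-primary endpoints for the two highest doses. "This family will be tested via the truncated Hochberg procedure, with truncation fraction pre-specified in the IAP". Section 8.5.2 reports 95% intervals, and "a subject with a missing response at Week 52, will be considered a non-responder".

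**The concern.** A truncated Hochberg family of four has no fixed 0.0125 share per endpoint. Its critical values depend on the rank of the p-value and on the truncation fraction. The list of changes in Appendix V explains the mismatch: 0.0125 per endpoint was formerly paired with a fixed high-to-low dose sequence, which supplied the control over doses. That sequence has been replaced; the 0.0125 sentence and the power built on it remain.

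Two things are at stake. The section on general considerations states a test level that does not by itself do what it says once more than one dose is tested. And the stated power describes a test that will not be run. Sections 5.1 and the Synopsis allow the primary cohort to be enlarged when drop-out erodes power, so the baseline figure should be the power of the planned test.

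**Working it through.** **Inputs.** From Section 8.1: n = 103 per group, about 51.5 in the HDA subgroup; SRI-4 0.40 vs 0.60; SRI-6 0.30 vs 0.55 (fallback 0.50). The protocol gives neither the correlation between the two test statistics nor the truncation fraction g. Correlation is taken as 0.6–0.7; a subject-level model with SRI-6 responders nested in SRI-4 responders gives about 0.6. g runs from 0 to 1. Power for a dose means rejecting at least one of its two endpoints.

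**1. Reproduce the stated figures (one-sided 0.0125, z = 2.241).** Power = Φ[(Δ − z·SE0)/SE1], with SE0 pooled and SE1 unpooled.
- SRI-4: SE0 = √(2×0.5×0.5/103) = 0.0697; SE1 = √((0.24+0.24)/103) = 0.0683; (0.20 − 2.241×0.0697)/0.0683 = 0.642, power 74.0%.
- SRI-6, +25 points: SE0 = √(2×0.425×0.575/51.5) = 0.0974; SE1 = √((0.21+0.2475)/51.5) = 0.0943; (0.25 − 2.241×0.0974)/0.0943 = 0.336, power 63.1%.
- SRI-6, +20 points: 43.1% in the same way.
- Either endpoint, bivariate normal: 80.5% and 76.3% at correlation 0.7; 82.2% and 77.6% at 0.6. Subject-level simulation: 81.6% and 77.2%.

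So 80% and 76% are right for a single dose under the 0.0125 rule.

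**2. Same n under the Section 8.5.2 family.** With ordered p-values and m = 4, the critical values are [g/(m−i+1) + (1−g)/m] × 0.025 one-sided. At g = 0 all four are 0.00625. At g = 1, the untruncated limit, they are 0.00625, 0.00833, 0.0125 and 0.025. The shared placebo gives a correlation of 0.5 between doses.

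| Scenario | Main | Fallback |
|---|---|---|
| Stated in Section 8.1 | 80% | 76% |
| One dose works, that dose, any g | 72–76% | 67–71% |
| Both work, per dose, g = 0 | 72–76% | 67–71% |
| Both work, per dose, g = 1 | 78–80% | 72–74% |
| Both work, at least one rejection | 86–89% | 82–86% |

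The lower ends come from the normal approximation at correlation 0.7, the upper ends from the subject-level simulation. On matching methods, the single-dose figure falls from 80.5% to about 72% (correlation 0.7), from 82.2% to about 74% (0.6) and from 81.6% to about 76% (simulation), a loss of 6 to 8 points. It hardly depends on g.

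**3. Error rate of 0.0125 per endpoint, used alone, one-sided.** One dose (two tests): 2.2–2.4%. Two doses: 4.0–4.3% (bound 4×0.0125 = 5.0%). Three doses: 5.5–6.0% (bound 6×0.0125 = 7.5%). Truncated Hochberg on the four hypotheses: about 2.2%.

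**4. Drop-out.** 108×0.95 = 102.6, so Section 8.1 treats drop-outs as lost sample. If the assumed rates are for completers only and the 5% are counted as non-responders, the rates become 0.38 vs 0.57 and 0.285 vs 0.5225. With 108 per group the 0.0125 rule still gives about 80%. The Section 8.5.2 family gives about 72% for a single effective dose and 86–87% for at least one rejection when both work.

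**The case against.** Four counter-arguments carry weight.

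- *Section 8.1 states its condition openly and its figures reproduce.* True. The fault is one of alignment: the condition is no longer the planned rule.
- *Section 8.5.1 defers to the multiple testing strategy.* True. A reader might infer that the protocol leaves the error rate uncontrolled at nearly 6%. It does not: that figure needs six unadjusted tests, which no section prescribes, and Section 8.5.2 controls the first family. What remains is a sentence claiming that 0.0125 per endpoint maintains 0.025, which is not so across doses.
- *The shortfall depends on the scenario.* True. A reader might infer that 80% is simply not delivered. Section 8.1 does not say whether 80% is per dose or for any dose. If both top doses work, the chance of at least one rejection exceeds 80%, and per-dose power comes close to 80% as g approaches 1. Leaving g to the IAP does not rescue the case where only one dose works.
- *The non-responder figures may count discontinuation twice.* This stands. Section 8.3.1 makes continued treatment part of the SRI definition, so the 40% and 60% may already include discontinuers. All 108 then count, and with both doses effective power is roughly 77–81% per dose and 90% for any rejection. The 72% is therefore conditional, and non-responder handling alone does not undo the stated power.

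Enlargement of the cohort is also triggered by drop-out, not by the 80% figure, so the effect on that decision is indirect.

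**Conclusion.** The conflict is in current text. Sections 8.1 and 8.5.1 and the power paragraph of the Synopsis use a per-endpoint, single-dose rule; Sections 5.1 and 8.5.2 and the testing paragraph of the Synopsis use a different one. The stated power is not the power of the planned test. The shortfall is clearest when only one of the two highest doses works, and small when both work and g is near 1; for at least one rejection with both effective there is none at 103 per group. These results rest on the Section 8.1 effect sizes, a 50% HDA share, an assumed endpoint correlation of 0.6–0.7 and unadjusted tests of proportions. The documents support neither an uncontrolled error rate nor an unconditional failure to reach 80%.

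**What to change.** - **Section 8.5.1:** replace the 0.0125 sentence with a reference to Section 8.5.2 as the only decision rule for the co-primary endpoints. Limit 97.5% intervals to the interim analysis. They should not be deleted outright, because Section 8.6 uses them there.
- **Section 8.1 and Synopsis:** restate the power under the truncated Hochberg family. Say whether it is per dose or for any rejection, which doses are assumed effective, and which truncation fraction and endpoint correlation were used.
- **Section 8.1:** state whether the assumed response rates already count discontinuers as non-responders. If not, give the power with drop-outs kept as non-responders.

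The cost is protocol wording and one re-run of the power calculation. No patients are added; the stated power becomes less favourable.

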## 8.5.2 Analysis of Primary Endpoints

The primary analysis of SRI-4 response at Week 52 among all subjects in the primary analysis cohort, and SRI-6 response at Week 52 among HDA subjects in the primary analysis cohort, will be an estimate of OR, together with associated two-sided 95% CI and p-value (testing null hypothesis  $H_0: OR = 1.0$ ), comparing each M2951 dose group to placebo, based on a logistic model for the odds of a given SRI response in the appropriate population, with M2951 dose group or placebo group as a factor and adjustment for covariates based on randomization strata. Additional covariates may be included in the model as specified in the IAP. In the primary analysis of SRI-4 or SRI-6 response at Week 52, a subject experiencing flare or CS dose increase during Weeks 41 to 52, or a subject with a missing response at Week 52, will be considered a non-responder.

The primary analysis of the co-primary efficacy endpoints will be based on the mITT analysis set, with supportive analyses based on the ITT and PP analysis sets, if the size of these analysis sets differ substantially ( $> 10\%$ ) from the size of the mITT analysis set.

The Family-Wise type 1 error rate (FWER) due to the co-primary endpoints and multiple M2951 dose group comparisons versus placebo will be controlled at the two-sided  $\alpha = 0.05$  level via a tree

gatekeeping procedure. The four hypotheses associated with the comparisons involving the co-primary endpoints and the two highest dose groups will form the first family of hypotheses in the tree. This family will be tested via the truncated Hochberg procedure, with truncation fraction pre-specified in the IAP. The multiple-testing procedure for the remainder of the tree, including the hypotheses associated with the comparisons involving the co-primary endpoints and the lowest dose group will be specified in the IAP.

A test for monotonic dose-response relationship, between ordered M2951 dose and SRI-4 response OR relative to placebo, will be performed as a supportive analysis. Similarly, a test for monotonic dose-response relationship, between ordered M2951 dose and SRI-6 response OR relative to placebo, will be performed as a supportive analysis in the HDA subgroup.

Descriptive statistics for SRI-4 response, and for SRI-6 response in the HDA subgroup, will be provided for each treatment group by time point.

Safety endpoints are considered to be primary endpoints in this study. Analysis of safety data is described in Section 8.5.4.

### **8.5.3 Analysis of Secondary Endpoints**

The analysis of secondary endpoints will be based on the mITT analysis set. Descriptive statistics for secondary endpoints will be provided by treatment group and time point.

The multiple-comparison procedure for testing the key secondary efficacy endpoints will be provided in the IAP. Other secondary efficacy endpoints will be analyzed for CCI [REDACTED].

#### **Key Secondary Endpoints**

Time to first severe (BILAG A) flare during the Treatment Period in all subjects will be compared between M2951 and placebo via a stratified log rank test. The adjusted hazard ratio comparing M2951 to placebo will be estimated (together with 95% CI) via a Cox regression model, with treatment group as a factor, and controlling for covariates defining randomization strata. A subject who discontinues treatment or completes treatment without experiencing flare will have his/her time to flare censored at the last time point at which flare could be assessed. A test for trend in dose-response, using the same Cox model, will be reported as a supportive analysis.

Kaplan-Meier estimates of probability of surviving free of severe (BILAG A) flare as a function of time on treatment will be provided for each treatment group.

The analysis of SRI-4 response at Week 52 among serologically active subjects will be an estimate of OR, together with associated 95% CI and p-value, comparing each M2951 dose group to placebo, based on a logistic model for the odds of SRI-4 response in the serologically active population, with M2951 dose group or placebo group as a factor and adjustment for covariates based on randomization strata. A test for trend in dose-response, using the same logistic model, will be reported as a supportive analysis.

Descriptive statistics for SRI-4 response in the serologically active subgroup, will be provided for each treatment group by time point.

### Other Secondary Endpoints

In the analysis of other secondary efficacy endpoints described in Section 8.3.2, binary endpoints will be modeled via logistic regression, time to event endpoints will be modeled via Cox regression and tested via stratified log rank test, continuous endpoints measured longitudinally will be analyzed using Mixed-effect Model for Repeated Measures (MMRM), and count endpoints (i.e., annualized flare rate) will be modeled via negative binomial regression, with treatment group as a factor, and adjusting for covariates defining randomization strata. Analysis of annualized flare rate will use the log of observation time (in years) as an offset in the model. Change in a binary endpoint between two time points will be analyzed via McNemar's test. The effect of treatment on change in a binary endpoint will be analyzed via logistic regression, with treatment group, time point, and interaction as predictors, and adjusting for covariates defining randomization strata. All tests of efficacy will be conducted at a two-sided  $\alpha$  level of 0.05, with p-values considered nominal unless generated as part of the tree gatekeeping multiple testing strategy as described in the IAP. P-values and the 95% CIs will be presented where applicable.

Change in SF-36v2 PCS and MCS scores (and their components) over time, change in LupusQoL score over time, change in FACIT-Fatigue score over time, and change in EQ-5D-5L index over time, will be compared between M2951 treatment groups and placebo based on change from Baseline using MMRM, with treatment group as a factor, and adjustment for Baseline and covariates defining randomization strata.

The PGIC score will be analyzed based on absolute score, using MMRM to account for subjects with missing data, with treatment group as a factor, and adjustment for covariates defining randomization strata.

In the analysis of each secondary efficacy endpoint, other covariates may be included in the model, as appropriate.

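### Baseline is a named covariate for the HRQoL change scores but not for the other by-visit change scores, and the HDA SRI-6 model has no working disease-activity covariate

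*Protocol*

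**What the plan says.** **Continuous secondary endpoints.** Protocol 8.5.3, Other Secondary Endpoints, gives a general rule for the outcomes listed in 8.3.2: "continuous endpoints measured longitudinally will be analyzed using Mixed-effect Model for Repeated Measures (MMRM", adjusted for treatment and the stratification factors. The next paragraph treats SF-36v2, LupusQoL, FACIT-Fatigue and EQ-5D-5L separately, "with treatment group as a factor, and adjustment for Baseline and covariates defining randomization strata". Section 8.3.2 also lists by-visit change in SLEDAI-2K, CLASI-A, BILAG-2004 and PGA. For these, Baseline is not named. The subsection ends by allowing further covariates where appropriate. The synopsis repeats the general rule, glosses it with HRQoL change as the instance, and names only the strata, so it does not carry the Baseline term that 8.5.3 gives HRQoL.

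**Co-primary endpoints.** Section 8.5.2 fits logistic models "with M2951 dose group or placebo group as a factor and adjustment for covariates based on randomization strata" and says the IAP may specify more covariates. The strata (8.2) are race, region and Screening SLEDAI-2K below 10 versus 10 or more. Sections 5.4 and 6.3 define HDA by the same cut. Section 8.3.1 scores SRI against Day 1 predose.

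**Power.** Section 8.1: "A sample size of 103 evaluable subjects per group provides 80% power at the" one-sided 0.025 level, where "each co-primary endpoint is tested via a chi-squared test of the odds ratio (OR) for treatment effect at the 0.0125 one-sided level".

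**The concern.** A change score depends on where the subject started. A model that leaves out the starting value has larger residual variance and leaves chance imbalance at Day 1 in the estimate. The authors name the term for one group of change scores and not for the adjacent group, without giving a reason.

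For SRI the link is built into the endpoint. SRI-6 needs a fall of at least 6 SLEDAI-2K points from Day 1, so a subject with a Day 1 score below 6 cannot respond. HDA status is fixed at Screening, normally up to four weeks earlier and in exceptional cases up to eight, and no minimum Day 1 score is set. Within HDA every subject has the same value of the disease-activity stratum. That leaves race and region as the only stated covariates that vary.

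At stake is precision for the change scores and power for the HDA co-primary test, which is the weaker of the two taken alone.

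**Working it through.** **1. Reproduce the stated power.** Inputs from 8.1: 103 per group; one-sided 0.0125 per test (z = 2.241); "an absolute improvement of 20% in Week 52 SRI-4 response proportion" from a 40% placebo rate; "an absolute improvement of 25% in Week 52 SRI-6 response proportion" from a 30% placebo rate; about half of subjects in HDA (51.5 per group).

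Power = Φ{[δ − z√(2p̄(1−p̄)/n)] / √[(p₀(1−p₀)+p₁(1−p₁))/n]}

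- SRI-4, 40% v 60%, n = 103: (0.200 − 2.241 × 0.0697)/0.0683 = 0.642, giving 74.0%.
- SRI-6 in HDA, 30% v 55%, n = 51.5: (0.250 − 2.241 × 0.0974)/0.0943 = 0.336, giving 63.1%.
- SRI-6 in HDA, 30% v 50%: 43.1%.

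The two tests share the HDA subjects, so their correlation is about √0.5 ≈ 0.7. The chance that at least one is significant is then 80.5% (25-point effect) or 76.3% (20-point effect). These match the stated 80% and 76%, and no covariate enters the calculation.

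**2. Change scores.** The correlation r between Day 1 and a later visit is not in the documents; 0.3 to 0.8 is assumed, with equal variances set to 1.

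- No Baseline-related covariate: variance 2(1 − r).
- Continuous Baseline: 1 − r².
- Ratio: (1 − r²)/[2(1 − r)] = (1 + r)/2.
- SLEDAI-2K, with a two-level stratum taken as a median split of the Baseline score: (1 − r)²(1 − 2/π) + (1 − r²).

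| r | Ratio, no stratum | Cut | Ratio, SLEDAI-2K stratum in model | Further cut |
|---|---|---|---|---|
| 0.3 | 0.65 | 35% | 0.836 | 16% |
| 0.5 | 0.75 | 25% | 0.892 | 11% |
| 0.8 | 0.90 | 10% | 0.961 | 4% |

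The left-hand cut applies to CLASI-A and PGA if the strata carry no information on their own Day 1 values; otherwise it is smaller. The right-hand cut treats the Screening stratum as if measured on Day 1; the earlier Screening score carries less information, so the gain for SLEDAI-2K may be somewhat larger.

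As an illustration, a two-sided 0.05 test with 60% power has noncentrality 1.960 + 0.253 = 2.213. Dividing by the square root of 0.65, 0.75 or 0.90 gives 78%, 72% or 65% power. The 60% is hypothetical, since the protocol does not power these endpoints.

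**3. HDA SRI-6.** Logistic simulation: 52 per arm, 30% v 55%, one-sided 0.0125, 4,000 trials per setting (Monte Carlo standard error √(0.63 × 0.37/4000) ≈ 0.8 point). The strength of Day 1 SLEDAI-2K is assumed.

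| Assumed log-odds per SD | Power without | Power with |
|---|---|---|
| 0.4 | 63% | 64% |
| 0.7 | 63% | 69% |
| 1.0 | 62% | 71% |

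A cruder route, effective n = 51.5/(1 − R²), gives 64.2%, 65.7% and 68.4% at R² of 0.02, 0.05 and 0.10.

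The mean standard error of the log odds ratio rises with the covariate, from 0.417 to 0.431 (at 0.4 per SD) and 0.475 (at 1.0 per SD). The gain comes from the effect size. The marginal log odds ratio is ln[(0.55/0.45)/(0.30/0.70)] = 1.05, and the odds ratio conditional on Day 1 score lies further from 1.

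**4. SRI-4, all subjects.** The Screening stratum is informative here. With it in the model, the continuous score adds about 0 to 3 points of power under the same assumptions.

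**The case against.** The strongest reply is that Section 8.5.1 presents the methods as an outline to be detailed in the IAP, that both 8.5.2 and 8.5.3 allow further covariates, and that the IAP is not at hand. This stands to the extent that omission is not established. A reader might infer that these endpoints will be analysed without Baseline and that precision is thrown away; the documents do not show that. They do show a stated covariate set that is uneven between adjacent paragraphs and has no disease-activity content in HDA. A permission to add covariates does not settle either.

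Four further limits stand:

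- A reader might infer that the sample size is undermined. It is not: the power statement assumes an unadjusted test and reproduces.
- A reader might expect narrower intervals for the SRI odds ratios. In logistic regression the prognostic covariate widens them on the log scale; the benefit is power.
- The 35% and 25% cuts should not be applied to SLEDAI-2K change, which already has partial adjustment through the Screening stratum.
- Corticosteroid dose is listed in 8.3.2 as change to Week 52, not by visit, so it is not clearly under the MMRM rule and is not part of this point.

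The synopsis gloss could be read as limiting the MMRM sentence to HRQoL. Section 8.5.3 has no such gloss and refers to the endpoints of 8.3.2 generally, so the wider reading is the natural one. On the narrow reading, the synopsis still omits the Baseline term that 8.5.3 gives HRQoL.

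It is also fair that the secondary p-values outside the gatekeeping procedure are nominal, and that a Day 1 score below 6 in HDA requires a fall of at least 5 points after Screening, whose frequency is unknown.

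**Conclusion.** The point holds as a gap in the stated models, not as an error in any stated figure. Section 8.5.3 secures Baseline adjustment for HRQoL only, and 8.5.2 secures no severity term for HDA SRI-6.

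The size rests on assumed correlations and prognostic strength. It could be material for CLASI-A and PGA at low to moderate correlation, is smaller for SLEDAI-2K, lies between about 1 and 9 power points for HDA SRI-6, and is slight for SRI-4. The case is strongest in HDA, where power alone is about 63% and the covariate is already collected.

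**What to change.** - **8.5.3:** state that every change-from-Baseline MMRM includes the Day 1 value and its interaction with visit, as a general rule covering SLEDAI-2K, CLASI-A, PGA and BILAG-2004 where scored numerically. Bring the synopsis into line.
- **8.5.2:** prespecify continuous Day 1 SLEDAI-2K total score as a covariate in the HDA SRI-6 model, with race and region, and drop the constant stratum there. Adding it to the all-subjects and serologically active SRI-4 models is optional. Note that the odds ratio is then conditional on Day 1 score.
- If the IAP already contains these terms, a cross-reference is enough.

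The cost is model wording in the protocol and IAP, settled before unblinding. No new data, visits or subjects are needed, and the sample size section does not change.
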